12 SAFETY AND TOLERABILITY

Safety will be assessed through analysis of AEs, clinical laboratory assessments, ECGs, vital signs, and physical examinations for the SAS using descriptive statistics. Observed case data will be used. Additionally, summaries of safety data will be displayed by treatment group. Treatment group will be based on the treatment each subject actually received regardless of the treatment group they were randomized to. All safety data will be presented in listings.

12.1 Adverse Events

AEs will be coded using MedDRA version 19.1. Except for the AE overview table and summaries of serious adverse events (SAEs) and AEs resulting in death (both of which will include all AEs), AE tables will only include summaries of treatment-emergent adverse events (TEAEs). A TEAE is defined as an AE with a start date on or after the first dose date and less than 30 days after the last dose date. If the AE start date is missing, the AE is assumed to be a TEAE. An AE overview table containing the frequency and percent of the following will be summarized by treatment group, treatment group within each stratum, and treatment group within each statin type (atorvastatin, rosuvastatin, simvastatin):

- Number of subjects with at least one TEAE, drug-related TEAE, SAE, and drug-related SAE;
- Number of subjects who discontinued study treatment due to a TEAE, drug-related TEAE, SAE, and drug-related SAE;
- Number of subjects who had a study treatment interruption due to a TEAE;
- Number of subjects who discontinued the study due to a TEAE; and
- Number of deaths and deaths due to a drug-related TEAE.

Additionally, the following will be summarized by treatment group, and treatment group within each stratum:

- TEAEs by system organ class (SOC) and preferred term (PT);
- TEAEs by PT (decreasing frequency in the gemcabene group);
- TEAEs by SOC, PT, and maximum severity;
- Related TEAEs by SOC and PT;
- Related TEAEs by PT (decreasing frequency in the gemcabene group);
- SAEs by SOC and PT;
- Related SAEs by SOC and PT;
- Discontinuation of study treatment due to TEAEs by SOC and PT;
- Discontinuation of study treatment due to related TEAEs by SOC and PT; and
- AEs that resulted in death by SOC and PT.

Summaries of SOC and PT will be sorted alphabetically by SOC and by decreasing frequency of PT in the gemcabene group.

If a subject has more than 1 TEAE at a given level (eg, SOC and PT), the subject will only be counted once within that level. When summarizing TEAEs by maximum severity or causality, at each level of summarization, subjects who report 1 or more TEAEs within that level are only counted once at that level using the event of greatest severity (in severity tables) or strongest relationship to study drug (in causality tables). All tables will show the number and percent of subjects with at least 1 TEAE (or SAE, per the criteria on the table). For example, the table of related SAEs will include a row for number and percent of subjects with at least one related SAE. Additionally, a drug-related TEAE is defined as a TEAE with an assigned relationship of “related.” A listing containing all AEs (pre-treatment and TEAEs) will be created; AEs that are not treatment-emergent will be flagged as non-treatment-emergent. Additionally, a listing containing AEs missing severity or relationship to the study drug will be provided; AEs that are not treatment-emergent will be flagged as non-treatment-emergent.

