8 SAFETY ASSESSMENTS

8.1 Adverse Events

An adverse event is defined as any untoward medical occurrence in a clinical investigation subject administered a pharmaceutical product, which does not necessarily have a causal relationship with this treatment. An adverse event can therefore be any unfavorable and/or unintended sign (including an abnormal laboratory finding), symptom, or disease temporally associated with the use of an investigational medicinal product, whether or not related to the investigational medicinal product. All adverse events, including observed or volunteered problems, complaints, or symptoms, are to be recorded on the appropriate eCRF.

Adverse events, which include abnormal and clinically significant clinical laboratory test variables, will be monitored and documented from the time of first dose of study drug (Day 1) until study participation is complete (the Follow-up Visit). Subjects should be instructed to report any adverse event that they experience to the Investigator. Beginning with the signing of the informed consent until the time of the first dose of study drug (Day 1), investigators should make updates to medical history and record any pre-existing medical condition or signs or symptoms that changes in severity, frequency, or seriousness in the medical history. Serious adverse events that occur prior to the first dose of study drug (Day 1) should be reported as an update to medical history as well as be reported on the appropriate adverse event eCRF. Beginning with the first dose of study drug (Day 1), investigators should make an assessment for adverse events at each visit and record all adverse events, non-serious and serious, on the appropriate adverse event eCRF.

Wherever possible, a specific disease or syndrome rather than individual associated signs and symptoms should be identified by the Investigator and recorded on the eCRF. However, if an observed or reported sign or symptom is not considered a component of a specific disease or syndrome by the Investigator, it should be recorded as a separate adverse event on the eCRF. Additionally, the condition that led to a medical or surgical procedure (e.g., surgery, endoscopy, tooth extraction, or transfusion) should be recorded as an adverse event, not the procedure. Concomitant procedures should be recorded as such on the appropriate eCRF.

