9.3.2 Analysis of Safety

No statistical analysis of safety data will be performed in this study. Safety will be assessed using the SAS with subjects included in the treatment group they actually received, regardless of their randomized treatment. The assessment of safety will include adverse events, clinical laboratory assessments, ECGs, physical examinations, and vital signs. Observed case data will be used.

Adverse events (AEs) will be coded using the most recent version of the Medical Dictionary for Regulatory Activities (MedDRA). The summarization of AEs will include only treatment-emergent AEs (TEAEs), defined as AEs that begin or worsen after randomization and ingestion of the first dose of study drug. TEAEs and SAEs will be summarized by system organ class (SOC), severity, and relationship to study drug for each treatment group. Deaths, withdrawal from study treatment due to AEs, and withdrawal from the study due to AEs will each be summarized by treatment group.

Safety laboratory data will be summarized by treatment group at baseline and at each post-baseline time point. Change from baseline to each time point, if appropriate, will also be summarized by treatment group. Baseline for safety laboratory data will be defined as the last pre-dose measurement (pre-dose Study Day 1/Visit T1 or prior). Frequency counts of new or worsening abnormalities will also be provided.

Vital signs data (value and change from baseline, where appropriate) will be summarized by treatment group at baseline and at each post-baseline time point. Baseline for vital signs data will be defined as the last pre-dose measurement (pre-dose Study Day 1/Visit T1 or prior). Abnormalities in ECGs and in PEs will be summarized.

All safety data will be listed.

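### By-arm SAE tables in SAP 12.1 count SAEs from before the first dose, and no planned table isolates treatment-emergent SAEs

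*SAP*

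**What the plan says.** **SAP 12.1** sets a general rule that "AE tables will only include summaries of treatment-emergent adverse events (TEAEs"), where a treatment-emergent event has "a start date on or after the first dose date and less than 30 days after the last dose date". It exempts the overview table and the summaries of SAEs and of fatal events, "both of which will include all AEs". The overview is shown by treatment group, by treatment group within stratum and by treatment group within statin type. The SAE and death tables are shown by treatment group and by treatment group within stratum. Events that are not treatment-emergent are to be flagged in the listings; no such flag or row is specified for the tables.

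**Protocol 9.3.2** (and the Synopsis) says "The summarization of AEs will include only treatment-emergent AEs (TEAEs"). Its meaning for that term covers events that start or get worse once the subject has been randomized and has taken a first dose. It then says "TEAEs and SAEs will be summarized by system organ class (SOC), severity, and relationship to study drug for each treatment group", and that deaths and withdrawals due to adverse events "will each be summarized by treatment group".

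**Protocol 8.1** says "Serious adverse events that occur prior to the first dose of study drug (Day 1) should be reported as an update to medical history" and, in the same sentence, requires them on the adverse event eCRF too. Sections 6.2 and 6.3 and Appendix A repeat this.

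**SAP section 8** lists five departures from the protocol. The scope of the adverse event tables is not among them.

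**The concern.** A by-arm SAE count is read as a comparison of what happened on gemcabene with what happened on placebo. An event before the first dose of either carries no information on that comparison, yet the SAP adds it to the arm's total. Since safety is descriptive, readers will judge the raw counts by eye, and SAE counts in a trial of 104 subjects over 12 weeks are likely to be small. One misplaced event can create an apparent imbalance or hide one. Safety within each statin stratum is a stated secondary objective, and there the denominators are halved. The overview also becomes internally inconsistent: a subject whose only event is a pre-dose SAE counts in the SAE row but not in the TEAE row beside it, so SAEs need not be a subset of TEAEs.

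**Working it through.** The plan states no figure on this point, so the check is mainly a comparison of texts, followed by a sense of scale.

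**1. Does a pre-dose SAE reach the tables?** It enters the adverse event data (Protocol 8.1), and SAP 12.1 expects this, since its full listing covers pre-treatment events. The safety set (SAP 7.1.3) holds only subjects given at least one dose. So the SAE is tabulated if, and only if, the subject is later randomized and dosed. Non-serious pre-dose events go to medical history and do not arise here.

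**2. Which outputs are exposed?**

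| Output in SAP 12.1 | Can it count a pre-dose event? |
|---|---|
| SAEs by SOC and preferred term | Yes |
| Overview, at least one SAE | Yes |
| Overview, TEAE rows | No, limited by their label |
| Related SAEs (table and overview) | Unlikely: Protocol 8.1.3 expects a related event to follow dosing |
| Stopping treatment due to an SAE | Unlikely: presupposes treatment |
| Deaths and fatal events | Only a fatal event that began before dosing in a subject later dosed |

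**3. Does another table give treatment-emergent SAEs by arm?** No. The TEAE tables are split by SOC, preferred term, maximum severity, relatedness and discontinuation, but not by seriousness. Severity (mild, moderate, severe) does not stand in for it.

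**4. What else does the exemption admit?** Events 30 or more days after the last dose. The Follow-up Visit falls 28 ± 3 days after the last dose, that is 25 to 31 days, so it can pick up an event at day 30 or 31. Protocol 8.3 also keeps later related SAEs reportable. Treatment could have caused these.

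**5. Scale of one event.** SAP 9.1 plans 26 subjects per arm per stratum, so 2 × 26 = 52 per arm. One subject is 1/52 = 1.9% of an arm and 1/26 = 3.8% of a stratum arm.

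**6. Share of SAE reporting time before dosing.** Pre-dose days come from SAP Table 1 and the wash-out lengths, and collection runs to Day 113. Share = pre / (pre + 113).

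| Wash-out | Pre-dose days | Share |
|---|---|---|
| None | 14 | 14/127 = 11% |
| 4 weeks | 14 + 28 = 42 | 42/155 = 27% |
| 6 weeks | 14 + 42 = 56 | 56/169 = 33% |
| 8 weeks | 14 + 56 = 70 | 70/183 = 38% |

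These are upper-end shares of calendar days, with consent on the earliest permitted day.

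**7. Chance of an uneven split.** The pre-dose SAE rate p among dosed subjects is an assumption, with 52 dosed per arm. Expected subjects per arm = 52p. P(at least one in the trial) = 1 − (1 − p)^104. P(unequal) = 1 − Σ [Bin(x; 52, p)]², summed over x from 0 to 52.

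| Assumed p | Expected per arm | At least one in trial | Unequal between arms |
|---|---|---|---|
| 0.5% | 0.26 | 40.6% | 36.5% |
| 1% | 0.52 | 64.8% | 54.5% |
| 2% | 1.04 | 87.8% | 69.8% |

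**The case against.** The strongest reply is that the SAP makes a legitimate inclusive choice. Showing every SAE and death hides nothing, and it keeps late events, which treatment may have caused, in the main tables. Cutting those tables down to treatment-emergent events could push late deaths to a listing. That stands, and the fix must respect it.

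A reader might infer that the SAP contradicts the protocol. The documents do not settle this. The protocol's sentence on TEAEs says only, but a later sentence in the same paragraph names SAEs beside TEAEs without that qualifier, and deaths are listed with no qualifier either. Naming SAEs separately would be redundant if they already had to be treatment-emergent. On the other side, SAEs are adverse events and the governing sentence is restrictive. The protocol is ambiguous, and the SAP chose a reading without saying so.

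It is also right that the harm is noise. Randomization on Day 1 is blinded and cannot depend on treatment, so pre-dose events favour neither arm in expectation. Eligibility thins them further: exclusion 10 covers major cardiovascular events with hospitalization within 3 months of Screening, exclusion 19 covers other compromising findings, and health changes are checked on Day 1. Not every SAE excludes a subject, however. The flagged listing lets a careful reader identify each event, but it does not correct the table that most readers will use.

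**Conclusion.** The point holds in a limited form. As written, the SAP counts pre-dose SAEs of dosed subjects by arm and stratum, mainly in two outputs, and offers no by-arm count of treatment-emergent SAEs. This sits poorly with the protocol's TEAE sentence without clearly breaching it, and section 8 is silent.

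Three further inferences are not supported. The death tables are barely exposed, since nobody who dies before dosing can be in the safety set. The events added are not all ones that treatment could not have caused, because late events come in too. The 11% to 38% shares are of days and not of SAEs; the top figure needs an 8-week wash-out plus a full screening period, and the documents do not say how many subjects that describes.

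The size is one subject in 52 (1.9%) or one in 26 (3.8%) per misplaced event. How often this would happen is unknown. The 36.5% to 69.8% chance of an uneven split rests wholly on an assumed rate of 0.5% to 2%. No efficacy result is affected. The change is worth making because it is cheap and sharpens the safety comparison.

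**What to change.** In SAP 12.1:

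- Tabulate treatment-emergent SAEs and fatal events by arm and by arm within stratum, and use the same definition for the overview's SAE row.
- Show pre-dose SAEs in a separate row or a listing.
- Give SAEs and deaths 30 or more days after the last dose their own row by arm, not a listing only.
- Reword the exemption: the word both follows three named items (overview, SAEs, deaths), so its reach is unclear.
- State how a pre-dose SAE that worsens after dosing is classified. The protocol's definition includes worsening, while the SAP's goes by start date.

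Record the chosen scope in SAP section 8. The change needs SAP wording and the non-treatment-emergent flag already planned for the listings. No new data are needed, and the only downside is a few extra table rows.

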12.2 Clinical Laboratory Assessments

Standard clinical laboratory evaluations for safety chemistry, coagulation, and hematology will be conducted at all study visits and the Follow-up Visit (only for subjects who had an abnormal result at Week 12 [or the ET Visit, if applicable] or an ongoing treatment-related AE). Clinically significant abnormal creatinine results at Week 12 (or the ET Visit, if applicable) will also be followed-up 2 weeks (\pm 3 days) after the last dose of study drug in addition to the 4 week (\pm 3 days) Follow-up Visit.

Additionally, a urine sample for urinalysis will be collected at the Pre-Screening Visit, if applicable, the Screening Visit, Day 1, Week 4, Week 8, Week 12, the Follow-up Visit (only for subjects who had an abnormal result at Week 12 [or the ET Visit, if applicable] or an ongoing treatment-related AE), and the ET Visit, if applicable. A urine microscopic examination will be performed when the dipstick result is abnormal (positive for blood, leukocyte esterase, or nitrites). Urine protein/creatinine ratio and albumin/creatinine ratio will be performed at the Screening Visit, Day 1, Week 4, Week 12, the Follow-up Visit (only for subjects who had an abnormal result at Week 12 [or the ET Visit, if applicable] or an ongoing treatment-related AE), and the ET Visit, if applicable. Urinary NGAL will be measured at Day 1, Week 4, Week 12, the Follow-up Visit (only for subjects who had an abnormal result at Week 12 [or the ET Visit, if applicable] or an ongoing treatment-related AE), and the ET Visit, if applicable.

The following laboratory parameters will be summarized at baseline and at each post-baseline time point by treatment group. Additionally, CFBL to each time point (including end of treatment), if appropriate, for each of the following laboratory parameters will also be summarized by treatment group. If, for a given subject at a given visit, the absolute count of neutrophils are not provided but segmented and band neutrophils are, segmented and band neutrophils are summed to determine the absolute count of neutrophils. If only segmented neutrophils are provided, they are used as the absolute count of neutrophils. Similarly, if neutrophils/leukocytes are not provided at a given visit but neutrophils (segmented)/leukocytes are, neutrophils (segmented)/leukocytes are used as neutrophils/leukocytes. If a laboratory value is lower or higher than the detection limit, the value will not contribute to summary statistics but will be included in the listings.

- **Chemistry:** ALT, albumin, ALP, AST, bicarbonate, BUN, calcium, chloride, creatine kinase (CK), creatinine, gamma-glutamyl transferase (GGT), glucose, lactate dehydrogenase (LDH), phosphorus, potassium, sodium, (total) bilirubin, (total) protein, estimated glomerular filtration rate (GFR)
- **Coagulation:** prothrombin time, activated partial thromboplastin time, international normalized ratio
- **Hematology:** hemoglobin, hematocrit, leukocytes, basophils, eosinophils, lymphocytes, monocytes, neutrophils, platelets, red blood cell count, mean corpuscular hemoglobin concentration, mean corpuscular hemoglobin, mean corpuscular volume
- **Urinalysis:** pH, specific gravity, NGAL, creatinine, protein, protein/creatinine ratio, albumin, albumin/creatinine ratio

Out-of-range values will be assessed using shift tables. Laboratory values will be identified as low, normal, or high based on the normal ranges provided by the central laboratory. Shift tables for each parameter will display, for each treatment group, the number of subjects with low, normal, and high values at baseline and end of treatment. Additionally, a summary will be provided of the number of subjects who shifted to high or low during the study. The denominators will be the number of subjects at risk for shifting, ie, the subjects at risk for shifting to low are those with high or normal values at baseline, and the subjects at risk for shifting to high are those with low or normal values at baseline.

Potentially clinically significant (PCS) tables will also be used to summarize out-of-range values for safety laboratory parameters. The PCS values are found in Table 3. The number and percent of subjects meeting the criteria below for single occurrences and consecutive (multiple) occurrences will be summarized by treatment group. The number and percent of subjects meeting the criteria below for single occurrences will be repeated for each statin-intensity stratum. Summaries will be given for any time post-baseline. The denominator for a given percentage will be the number of subjects who had a post-baseline assessment for the corresponding parameter. Additionally, for subjects with at least 1 post-baseline laboratory value meeting the PCS criteria, all laboratory values will be provided in a listing.

Table 3. Lab PCS Criteria

Laboratory Parameter	Unit	PCS Criteria
ALT	U/L	> 2 × ULN
AST	U/L	> 2 × ULN
BUN	mg/dL	> 2 × ULN
Creatine kinase	U/L	> 3 × ULN
Creatinine	mg/dL	> 0.3 increase from baseline
Estimated GFR	mL/min	Decrease > 15 from baseline
Hemoglobin	g/dL	Decrease > 1.5 from baseline
Urinalysis Parameter	Unit	PCS Criteria
Blood	-	present
Protein (qualitative)	-	present
Protein (quantitative)	-	> ULN
Protein/creatinine ratio	mg/mmol	> ULN

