Phase 1 pharmacokinetic (PK) studies have demonstrated that gemcabene is rapidly absorbed following oral administration, with exposure increasing approximately linearly with dose. No clinically meaningful drug-drug interactions have been observed with simvastatin (80 mg), atorvastatin (80 mg), or digoxin (0.25 mg). No clinically relevant effect on QTc or blood pressure has been observed.

Across all clinical studies, the majority of treatment-emergent adverse events were mild to moderate in intensity. The most common adverse events reported included headache, asthenia (feeling of weakness), nausea, dizziness, dyspepsia (upset stomach), infection, abnormal bowel movements, myalgia, and abnormal kidney function tests. Ten healthy adult subjects reported a treatment-emergent serious adverse event (SAE) across all previous studies. None of these SAEs were considered treatment-related. There were no deaths.

Small mean increases in serum creatinine and blood urea nitrogen (BUN) have been observed in some studies. These changes appeared within the first 2 to 4 weeks and did not appear to increase further over time. An iohexol clearance study showed that glomerular filtration rate (GFR) decreased slightly and was associated with a slight increase in serum creatinine. There was no indication of proteinuria or hematuria identified in any subject. There were no significant changes observed in urine protein, which seems to indicate that gemcabene does not cause tubular or glomerular injury. And, the increase was reversible with all creatinine values returning to baseline within approximately 2 weeks of cessation of gemcabene, suggesting a vascular effect and not renal injury.

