8.1.4.2 Creatinine increase

If, at any visit, a creatinine increase >0.3 mg/dL (27 μ mol/L) from baseline or a GFR decrease of >15 mL/min from baseline is observed, a repeat chemistry will be performed. The subject's past medical history, concomitant medications (including over the counter drugs and herbal supplements), and any recent symptoms (e.g., fatigue, malaise, polyuria/oliguria, or palpitations) will be reviewed to determine a potential etiology and make a clinical assessment of the significance of the finding.

During the study, clinically significant abnormal results in NGAL will be used as a means of identifying subjects who have unremarkable creatinine/BUN values at the time of assessment but may require additional or closer/follow-up monitoring of renal studies.

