6.3 Safety Measures

Safety and tolerability measures include adverse events (AEs), safety laboratory parameters (chemistry, hematology, coagulation, and urinalysis), 12-lead electrocardiograms (ECGs), physical examinations, vital signs, and weight. Regarding safety laboratory parameters, particular attention will be paid to hepatic (eg, alanine aminotransferase [ALT]/aspartate aminotransferase [AST], bilirubin, alkaline phosphatase [ALP]), renal (eg, blood urea nitrogen [BUN], serum creatinine, protein/creatinine ratio, albumin/creatinine ratio, neutrophil gelatinase-associated lipocalin [NGAL], urinalysis sediments, pH, electrolytes), and skeletal muscle (ie, creatine kinase) toxicities. AEs will be coded using the Medical Dictionary for Regulatory Activities (MedDRA) version 19.1.

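### SAP 12.2 drops laboratory values beyond a detection limit from summary statistics, so safety summaries by visit and change describe only quantifiable values and can distort the comparison between arms in either direction

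*SAP*

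**What the plan says.** SAP 12.2 plans summaries of all listed chemistry, coagulation, hematology and urinalysis parameters at baseline and each later time point, and of change from baseline. In the same paragraph it says that a value "lower or higher than the detection limit, the value will not contribute to summary statistics but will be included in the listings". The urinalysis list is "pH, specific gravity, NGAL, creatinine, protein, protein/creatinine ratio, albumin, albumin/creatinine ratio".

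Three other parts of the SAP fix what this means:

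- Section 9.2 summarizes continuous variables by mean, SD, median, minimum and maximum.
- Section 9.2 computes change only where a baseline and a post-baseline value both exist.
- Section 9.4 uses observed cases for safety, so nothing replaces an excluded value.

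Neither document gives a substitution rule, a count of excluded values or a censored-data method. Protocol 9.3.2 plans the same visit and change summaries without this exclusion.

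Separate displays exist. SAP 12.2 has shift tables, and "a summary will be provided of the number of subjects who shifted to high or low during the study". For the PCS tables, "The denominator for a given percentage will be the number of subjects who had a post-baseline assessment for the corresponding parameter". The plan does not say how values beyond a limit enter either display.

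**The concern.** Dropping a value because it is very low or very high selects on the outcome being summarized. If the drug changes how many values can be quantified, the two arms are trimmed differently and their summaries no longer describe comparable subjects.

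The markers most plausibly exposed are urinary. SAP 6.3 singles out renal measures including "albumin/creatinine ratio, neutrophil gelatinase-associated lipocalin [NGAL], urinalysis sediments, pH, electrolytes", and Protocol 8.1.4.2 says "clinically significant abnormal results in NGAL will be used as a means of identifying subjects who have unremarkable creatinine/BUN values". NGAL has one scheduled pre-dose sample, at Day 1 (Protocol 8.6), so an undetectable Day 1 result removes that subject from every NGAL change summary. A subject who moves from undetectable to detectable has no change value. The rule also works upward: a result above an upper limit cannot appear in the mean or the maximum.

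The numeric tables would not show how many values were left out.

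**Working it through.** **What can be checked.** The plan states no figure for this point, so there is none to reproduce. The calculation below shows only what the rule does; every input is assumed.

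**Inputs (assumed).** Placebo marker Y = exp(0.9 Z) with Z standard normal, so the median is 1 and the log-SD is 0.9. Correlation between visits is 0.6 on the log scale. One lower limit L sits at the 30th percentile of baseline: L = exp(0.9 × -0.5244) = 0.624. Without exclusions the placebo mean is exp(0.9²/2) = 1.499.

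**Visit mean after exclusion.** The mean of Y among values at or above c is

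m(c) = 1.499 × Φ(0.9 - ln c/0.9) / Φ(-ln c/0.9).

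- Placebo, c = 0.624: 1.499 × 0.9228/0.700 = 1.976.
- Uniform doubling, retained when Y ≥ 0.312: 2 × 1.499 × 0.9859/0.9023 = 3.276. Difference 3.276 - 1.976 = 1.30.
- Additive 0.75: every active value exceeds 0.624, so none is dropped. The mean is 1.499 + 0.75 = 2.249. Difference 0.27.
- Additive 0.30, retained when Y ≥ 0.324: 0.30 + 1.499 × 0.9843/0.8949 = 1.949. Difference -0.03.
- Fourfold in 20% of subjects: (0.2 × 4 × 1.499 × 0.9985 + 0.8 × 1.499 × 0.9228) / (0.2 × 0.9805 + 0.8 × 0.700) = 2.304/0.756 = 3.05. Difference 1.07.

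**Mean change after exclusion.** A pair counts only if both values are quantifiable. This was simulated with 3,000,000 pairs per arm.

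| Assumed effect | True difference | Visit | Change |
|---|---|---|---|
| None | 0 | 0 | 0 |
| Uniform doubling | 1.50 | 1.30 | 1.78 |
| Additive 0.75 | 0.75 | 0.27 | 0.61 |
| Additive 0.30 | 0.30 | -0.03 | 0.19 |
| Fourfold in 20% of subjects | 0.90 | 1.07 | 1.25 |

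The visit difference can be too small, too large or of the wrong sign, and the change difference too small or too large.

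**Dependence on the censored share.** At 10%, 30% and 50% undetectable:

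- Doubling gives visit differences of 1.41, 1.30 and 1.21, and change differences of 1.59, 1.78 and 2.00.
- Additive 0.75 gives change differences of 0.72, 0.61 and 0.43; its visit difference at 50% is -0.11.

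**Scale against sampling error.** For the doubling case with 52 complete subjects per arm, the standard error is 0.52 (visit) and 0.46 (change). At 30% undetectable the bias is (1.50 - 1.30)/0.52 = 0.4 standard errors for the visit mean and (1.78 - 1.50)/0.46 = 0.6 for change.

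**Subjects lost.** With no drug effect, 84%, 57% and 35% of pairs remain in each arm at 10%, 30% and 50% undetectable. At 30%, subjects undetectable at baseline and detectable later are 12.7% of each arm with no effect, and 22.8% of the active arm under doubling.

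**Medians are not protected once values are dropped.** In a separate illustration (log-SD 1, same correlation, active shift 0.4 on the log scale), the true difference in visit medians of 0.50 falls to about 0.45, 0.40 and 0.37.

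**The case against.** The strongest reply is that nothing in the documents shows the rule will bite. No detection limit or censored fraction is given, and the exposure of NGAL, albumin and protein is plausible rather than documented. Protocol 1.3 reports of earlier studies: "There were no significant changes observed in urine protein, which seems to indicate that gemcabene does not cause tubular or glomerular injury". If few values are censored, or the drug does not move the marker, the comparison is intact. This stands, and it is why the size is left open.

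Second, other displays carry some of the information. All values are listed, shift tables and the count of shifts use laboratory normal ranges, and Table 3 covers quantitative protein and the protein/creatinine ratio. Clinically significant abnormalities are recorded as adverse events (Protocol 8.1). Protocol 8.1.4.2 uses NGAL for individual subjects during the study, which does not depend on summary tables. This stands in part. Shift tables show no magnitude, listings do not compare arms, and Table 3 has no criterion for NGAL or the albumin/creatinine ratio. End of treatment is defined as the last non-missing value (SAP 9.2), and the SAP does not say whether a censored value counts as missing.

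Third, half-limit substitution is one convention among several. This also stands. On a normal marker with mean 5 and SD 1, it turns a true 0.50 into 0.58 to 0.78. The remedy therefore rests first on the censored counts.

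A reader might go further and infer that the rule always understates visit differences and overstates change, or that it cannot reverse a sign. The table refutes both: these patterns belong to a uniform multiplicative effect, and the documents do not say what form an effect would take.

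**Conclusion.** The concern holds as a minor point. SAP 12.2 states a rule that selects on the outcome, and with SAP 9.2 and 9.4 it leaves visit and change summaries describing quantifiable values only, with no count of what was removed. Where values are censored and the drug moves the marker, the between-arm difference is distorted. The illustrative sizes rest wholly on the assumed distribution, visit correlation, censored share and form of effect; the true size may be nil.

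Two inferences go beyond the text. One is that a renal signal would be hidden: the documents report no such signal, and the values remain in listings and may still be counted in the shift and PCS tables, since the exclusion names only summary statistics. The other is that efficacy results are affected: the rule stands in the safety section, and the plan does not extend it to efficacy markers. Safety has no inferential analysis (Protocol 9.3.2), so no test, decision rule or sample size changes.

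**What to change.** Replace the sentence in SAP 12.2 with:

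> Values beyond a detection limit are retained. The number and percent beyond each limit are reported by treatment group and visit, and these values are classified in the shift and PCS tables. For by-visit and change-from-baseline summaries, values below the lower limit are set to half that limit and values above the upper limit to that limit, with the median as the main summary; where 50% or more of an arm's values at a visit are beyond a limit, the censored proportion is the main summary. For ratios to creatinine, the substitution is made in the censored component where component results are available; otherwise only the censored count is reported.

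The ratio clause is needed because a ratio with a censored numerator has no single limit: its bound varies with each subject's urine creatinine.

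The cost is one SAP paragraph and a programming rule. No new measurements are needed, but the documents do not say whether component results and their limits are in the laboratory data, hence the fallback to counts. Substituted values are approximate and depend on the marker's distribution, and capping at an upper limit still understates extremes. A visit median does not depend on the value substituted below a lower limit while fewer than half of the values lie there, but a median change can. The censored counts must therefore accompany every such summary.
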